4.2.2 The Columbia Suicide Severity Rating Scale (C-SSRS)

Brief description: The Columbia Suicide Severity Rating Scale (C-SSRS) is a joint interview with the caregiver and patient that systemically assesses suicidal ideation and suicidal behavior (Posner et al, 2007). This scale will be administered at Screening Visit to evaluate life time suicide attempt, suicide behaviors, and other non-suicidal self-injuries. Positive responses on the C-SSRS will be mapped to the Columbia Classification Algorithm of Suicide Assessment (C-CASA) for classification and reporting using a standard algorithm.) . In TTP488-303, the C-SSRS will be conducted at Months 3, 6, 9, 12, 15, 18, 21 and 24 or in the event of early termination.

- Range: The following outcomes are C-SSRS categories and have binary responses (yes/no). The categories have been re-ordered from the actual scale to facilitate the definitions of the composite and comparative endpoints, and to enable clarity in the presentation of the results.
 - Category 1 – Wish to be Dead
 - Category 2 – Non-specific Active Suicidal Thoughts
 - Category 3 – Active Suicidal Ideation with Any Methods (Not Plan) without Intent to Act
 - Category 4 – Active Suicidal Ideation with Some Intent to Act, without Specific Plan
 - Category 5 – Active Suicidal Ideation with Specific Plan and Intent
 - Category 6 – Preparatory Acts or Behavior
 - Category 7 – Aborted Attempt
 - Category 8 – Interrupted Attempt
 - Category 9 – Actual Attempt (non-fatal)
 - Category 10 – Completed Suicide

Self-injurious behavior without suicidal intent is also a C-SSRS outcome (although not suicide-related) and has a binary response (yes/no).

The following outcome is a numerical score derived from the C-SSRS categories. The score is created at each assessment for each patient and is used for determining treatment emergence.

Suicidal Ideation Score: The maximum suicidal ideation category (1-5 on the C-SSRS) present at the assessment. Assign a score of 0 if no ideation is present.

Endpoints:

Composite endpoints based on the above categories are defined below.

- **Suicidal ideation:** A “yes” answer at any time during treatment to any one of the five suicidal ideation questions (Categories 1-5) on the C-SSRS.
 - **Suicidal behavior:** A “yes” answer at any time during treatment to any one of the five suicidal behavior questions (Categories 6-10) on the C-SSRS.
 - **Suicidal ideation or behavior:** A “yes” answer at any time during treatment to any one of the ten suicidal ideation and behavior questions (Categories 1-10) on the C-SSRS.
- Comparative endpoints of interest are defined below. “Treatment emergence” is used for outcomes that include events that first emerge or worsen. “Emergence” is used for outcomes that include events that first emerge.

4.2.3 Vital Signs

Vital signs measurements consist of blood pressure and pulse rate. . In TTP488-303, the vital signs will be conducted at Months 3, 6, 9, 12, 15, 18, 21 and 24 or in the event of early termination. Variables of analysis will include means, mean changes over time, and proportions of subjects meeting criteria for potential clinical concern in vital signs:

- Mean and mean changes in systolic and diastolic blood pressures
- Mean and mean changes in pulse
- Proportions of subjects with treatment-emergent values or changes of potential clinical concern.

4.2.4 Clinical laboratory assessments

Routine clinical laboratory data will be summarized with descriptive statistics on assessment values and change from Baseline. Routine clinical laboratory data will also be evaluated on the basis of laboratory-defined reference ranges and clinically important values or changes, as defined in this document (Section 10). Routinely collected laboratory safety data that are not required by the protocol will be considered source data, and will not be captured for inclusion into the study database. In TTP488-303, the clinical laboratory blood samples will be collected at Months 6, 12, 18 and 24 or in the event of early termination.

Definition:

- A treatment-emergent abnormal value (TEAV) is a laboratory value that is abnormal after administration of study medication that was normal prior to study medication administration.
- A TEAV of potential clinical concern is a value or change that meets criteria specified in this SAP in Section 10.

Laboratory analytes in this study include:

- Hematology
 - Hemoglobin
 - Hematocrit
 - Erythrocyte (RBC) count
 - Platelet count
 - Total leukocyte (WBC) count
 - MCV
 - Leukocyte differential (percent and total)
 - Total neutrophils
 - Eosinophils
 - Monocytes
 - Basophils
 - Lymphocytes
- Clinical chemistry
 - BUN
 - Creatinine
 - Glucose
 - HbA1c
 - Calcium
 - Sodium
 - Potassium
 - Chloride
 - Bicarbonate
 - AST
 - ALT
 - GGT
 - LDH
 - Total bilirubin
 - Alkaline phosphatase
 - Uric acid
 - Albumin
 - Total protein

Safety variables of analysis include:

- Subjects with TEAVs
- Subjects with TEAVs of potential clinical concern (based on criteria in this SAP)
- Subjects with a TEAV in a liver function test (LFT)

4.3 Pharmacokinetics and Pharmacodynamics Variables

Blood samples for pharmacokinetic (PK) analysis will be collected prior to dosing at Baseline (Month 18 of TTP488-301), Months 6, 12, 18 and 24 or at Early Termination.

Blood samples for plasma A β (total, 1-40 and 1-42) biomarkers analysis will be collected prior to dosing on Baseline (Month 18 of TTP488-301), Months 6, 12, 18, and 24 or at Early Termination.

4.4 Adverse Events of Special Interest

Adverse events related to signs and symptoms of AD potentially pertain to efficacy as well as safety of the compound. Analysis of prior study data suggest the potential abatement of the signs and symptoms of AD that are associated with worsening of AD. Specifically, TEAEs classified by MedDRA into the SOC for psychiatric disorders (at the SOC level within the hierarchy of MedDRA) and specifically high-level group terms (HLGTs) of anxiety disorders and symptoms (at the HLGT level within the hierarchy of MedDRA) will be variables of interest for comparison.

5 Statistical Methodology

General statistical methods will be applied as appropriate for out-patient, open-label clinical studies. Safety evaluations will rely on descriptive statistics. Randomization groups from TTP488-301 will be examined to delineate between subjects who received placebo during TTP488-301 and those who received TTP488 during TTP488-301. For the purpose of this SAP, these groups will be considered “treatment groups” acknowledging that all subjects receive open-label azeliragon in this study.

Continuous variables will be summarized using mean, median, standard deviation, minimum, maximum, and number of subjects available for analysis. Categorical variables will be summarized using frequency, proportion, and number of subjects available for analysis.

Baseline will be the latest available data point prior to start of treatment in TTP488-303.

Data displays will include the following designations for treatment groups:

- Subjects randomized to azeliragon in TTP488-301
- Subjects randomized to placebo in TTP488-301
- All subjects.

SAS Version 9.4 or later will be used. Medical dictionary for Regulatory Activities (MedDRA) Version 18.0 or later will be used for coding adverse events. Medications will be coded using WHO Drug Dictionary (WHODD) Version March 2009 or later.

5.1 Statistical Methodology for Efficacy Analysis

Efficacy evaluation will include the co-primary variables of analysis (ADAS-cog and CDR-sb), key secondary measures, and other efficacy markers.

Statistical analysis will be considered descriptive analysis. No alpha is allocated for this study.

5.1.1 Statistical Methodology for Primary Efficacy Analysis

The primary descriptive analysis will be done on change from baseline in ADAS-cog and on change from baseline in CDR-sb.

Analysis of covariance (ANCOVA) will be done to compare those patients who were randomized to azeliragon in TTP488-301 with those who were randomized to placebo. The ANCOVA will include baseline measure as a covariate and treatment arm from TTP488-301; a main-effects model will be used.

Descriptive analysis will be applied to those patients who were treated with placebo in TTP488-301 to compare the profile during TTP488-301 with that of the profile in TTP488-303.

Descriptive statistics will be applied to the total patient population without regard for prior treatment.

Analyses will include data from the 18-month period from TTP488-301 with continuation for the available visit data from TTP488-303.

Additional supportive analyses will be done for which data displays are not planned.

Descriptive summaries will be produced of the observed values and change from Baseline in efficacy variables by treatment group at each individual time point and at endpoint (final on-treatment assessment for each subject).

For statistical analyses, 95% confidence intervals will be produced for the least-squares means (LSM) in each treatment group.

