9.0 DATA ANALYSIS/STATISTICAL METHODS

The statistical considerations summarized in the following subsection outline the plan for data analysis of this study. A final and complete Statistical Analysis Plan (SAP) will be finalized prior to database lock for the study. The SAP will supersede the protocol. Any deviations from the planned analyses will be described in the final integrated study report.

This open-label, single-arm study includes subjects who completed TTP488-301, in which they were randomized to receive azeliragon (plus SoC) or placebo (plus SoC). An analysis plan for the meta-analysis combining data from TTP488-301 with this study will be done prior to database lock for this study. It is intended that the key analysis of results from this open-label study be described in the integrated analysis plan, and that the analysis of this study alone be described in this protocol.

SAS Version 9.4 or later will be used. Medical dictionary for Regulatory Activities (MedDRA) Version 18.0 or later will be used for coding adverse events. Medications will be coded using WHO Drug Dictionary (WHODD) Version March 2009 or later.

Continuous data will be summarized using descriptive statistics (number, mean, median, standard deviation, first and third quartiles, minimum, and maximum). Categorical data will be summarized for the enrolled population and also by treatment group according to the randomization of TTP488-301 using frequency tables (frequencies and percents).

Baseline will be the latest available data point prior to the first dose of study medication in this study (start of treatment for this protocol).

Outliers that are detected during the review of the data will be investigated. Methods for dealing with outliers will be defined in the SAP. In general, missing data will not be imputed, and outliers will not be excluded unless they are considered to be erroneous values.

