1.9 Modifications from the Statistical Section of the Protocol

There are no modifications from the Statistical Section of the Protocol.

2 Statistical Hypotheses

There are no formal statistical hypotheses for this open-label study.

3 Populations of Analysis

In accordance with guidance from the International Conference of Harmonization of Technical Requirements for Registration of Pharmaceuticals for Human Use (ICH) guideline ICH E9 Statistical Principles for Clinical Trials (1998), the following population of analysis will be used for all statistical analysis:

- The full analysis set (FAS) includes all randomized subjects who receive any study medication and have at least one post-Baseline assessment.
- The per protocol set (PPS) includes all subjects in the FAS, except for those who are excluded because of major protocol violations, where a major protocol violation is one that may affect the interpretation of study results (e.g., taking less than 50% of prescribed study medication during participation).

Final determinations of the PPS will be made at the final data review meeting (DRM) held in accordance with ICH E9 prior to the lock data.

- The safety set (SAF) includes all patients who received at least one dose of study medication. The SAF is used for all safety analyses.

The FAS is used for efficacy analysis; the SAF will be used for safety analyses.

It is noted that if the FAS and PPS do not differ by more than 15% in numbers of individuals, analysis may be limited to FAS.

4 Variables of Analysis

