6.1 Definition of Baseline

Two baselines will be used in this study: (1) the latest assessment prior to the first dose of double-blind study drug, and (2) the latest assessment prior to the first dose of open-label study drug. For safety evaluations, the Baseline assessment for all measurements will be the latest available, valid measurement taken prior to the initiation of study medication in TTP488-303.

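### The between-arm efficacy ANCOVA, read with the baseline in SAP Section 5, adjusts for the TTP488-301 Month 18 score, so a maintained benefit and no effect both come out near zero; SAP 6.1 does not say which baseline efficacy uses

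*SAP*

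**What the plan says.** SAP 5.1.1 analyses change from baseline in ADAS-cog and CDR-sb by ANCOVA, comparing subjects by their randomized arm in TTP488-301. On the model it says: "The ANCOVA will include baseline measure as a covariate and treatment arm from TTP488-301; a main-effects model will be used".

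Baseline is described in several places:

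- SAP Section 5: "Baseline will be the latest available data point prior to start of treatment in TTP488-303".
- Protocol 9.0: "Baseline will be the latest available data point prior to the first dose of study medication in this study". Protocol 9.4, the efficacy section, repeats the rule in shorter form.
- Protocol 6.1.1 makes the TTP488-301 Month 18 assessments the baseline assessments of this extension.
- SAP 6.1: "Two baselines will be used in this study: (1) the latest assessment prior to the first dose of double-blind study drug", the second being the last assessment before open-label dosing. It then assigns one use only, giving safety the open-label value: "For safety evaluations, the Baseline assessment for all measurements will be the latest available, valid measurement taken prior to the initiation of study medication". Nothing is assigned to efficacy.
- SAP 1.9: "There are no modifications from the Statistical Section of the Protocol".

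SAP 5.1.1 also brings the 18 months of TTP488-301 data into the analyses without naming the anchor. SAP 5.1.2 carries the same kind of model to MMSE, ADCS-ADL, NPI and plasma Aβ, and plans an ANCOVA on DEMQOL-Proxy with its own baseline as covariate. On precision, 5.1.1 says "95% confidence intervals will be produced for the least-squares means (LSM) in each treatment group"; no interval is stated for the difference between arms.

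**The concern.** Everyone takes azeliragon in TTP488-303, so the contrast between TTP488-301 arms is earlier start against delayed start. Under the Section 5 definition, both the reference value and the covariate are Month 18 scores, which randomized treatment may already have changed. Adjusting for them takes out most or all of any difference built up in TTP488-301.

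A benefit that is fully kept then looks like no effect. A benefit that disappears because former placebo subjects catch up looks like a difference of several points against the azeliragon-first group. This ANCOVA is the SAP's only adjusted comparison of the two groups, and a secondary objective is the time course of azeliragon's effect on ADAS-cog and CDR-sb.

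Because 6.1 leaves the efficacy baseline open, two programmers could both follow this SAP and report different estimates.

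**Working it through.** The plan states no power, alpha or expected difference for this comparison, so there is no figure of its own to reproduce.

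**Inputs from the documents.** Phase 2 ADAS-cog differences at Month 18 of 3.1 (all patients) and 4.0 (mild AD), and a CDR-sb difference of 1.0 (mild AD), all from protocol 1.1.3. Baseline falls 18 months after TTP488-301 entry.

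**Assumed, because the documents give no values.** Entry true-score SD 7; individual slope SD s = 0.10, 0.15 or 0.20 points per month, independent of entry score; measurement-error SD e = 3 or 4; assessment at t = 24, 30, 36 or 42 months after TTP488-301 entry (extension Months 6 to 24); no selection among those who enrol.

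**Step 1: what the model estimates.** Let D be the arm difference (azeliragon-first minus placebo-first; higher ADAS-cog is worse, so negative favours azeliragon-first). Let b be the within-arm regression slope of the later score on the Month 18 score. ANCOVA on change gives

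(D_end − D_18) + (1 − b) × D_18 = D_end − b × D_18.

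**Step 2: range of b.** b = (49 + 18 × t × s²) / (49 + 324 × s² + e²).

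- Smallest (s = 0.10, e = 4, t = 24): (49 + 4.32) / (49 + 3.24 + 16) = 53.32 / 68.24 = 0.78.
- Largest (s = 0.20, e = 3, t = 42): (49 + 30.24) / (49 + 12.96 + 9) = 79.24 / 70.96 = 1.12.

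**Step 3: three scenarios.**

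| Scenario | D_18 | D_end | Month 18 baseline | Pre-double-blind baseline |
|---|---|---|---|---|
| No effect | 0 | 0 | 0 | 0 |
| Benefit fully maintained | −3.1 or −4.0 | same as D_18 | −0.87 to +0.47 | about −3.1 or −4.0 |
| Full placebo catch-up | −3.1 or −4.0 | 0 | +2.42 to +4.47 | about 0 |

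The extremes of the maintained row are −4.0 + 0.78 × 4.0 and −4.0 + 1.12 × 4.0, using unrounded b. Those of the catch-up row are 0.78 × 3.1 and 1.12 × 4.0. For a maintained CDR-sb benefit of 1.0, b from 0.8 to 1.1 leaves −0.20 to +0.10.

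**Step 4: simulation check** (n = 400,000 per setting, benefit 4.0, fitting change on arm and baseline).

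| Setting | Baseline | Maintained | Catch-up |
|---|---|---|---|
| s = 0.10, e = 4, t = 24 | Month 18 | −0.89 | +3.12 |
| | Pre-double-blind | −4.03 | 0.00 |
| s = 0.20, e = 3, t = 36 | Month 18 | +0.22 | +4.21 |
| | Pre-double-blind | −3.97 | −0.01 |

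**Step 5: different variance assumptions** (entry SD 7, error SD 3, 18-month decline SD 4, extra follow-up SD 5; 100 or 200 per arm; 400 trials per scenario; b about 0.87 to 1.17; benefit 3.1). The Month 18 anchor gives −0.46 to +0.51 for a maintained benefit, −0.01 to +0.09 for no effect and +2.66 to +3.64 for catch-up. The pre-double-blind anchor gives −3.20 to −3.07, −0.04 to +0.10 and −0.03 to +0.07.

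**The case against.** The strongest reply is that SAP 6.1 already points the other way. It introduces a pre-double-blind baseline, restricts only safety to the open-label one, and sits in a SAP that takes precedence over the protocol. If efficacy also used the open-label value, the first baseline would have no evident use. That reading is plausible, but SAP Section 5 states the open-label definition without exception and SAP 1.9 claims no departure from the protocol. The ambiguity is certain; the adverse reading is the one written down most directly.

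A second reply is that change from the open-label start answers a legitimate question: do the groups diverge or converge once all are treated? For that question, near zero under a kept gap is correct. But divergence after rollover is D_end − D_18, and this ANCOVA returns it only when b = 1. The unadjusted difference in change would answer it directly.

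Other points stand as limits on the weight:

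- Efficacy is secondary and descriptive, with no alpha.
- Observed values are also planned: "Descriptive summaries will be produced of the observed values and change from Baseline in efficacy variables by treatment group at each individual time point". These would show a maintained gap, though without an adjusted difference or interval.
- Protocol 9.0 sends the key analysis to an integrated plan that is not among these documents and may address the question.
- SAP 1.5 says the study ended early, so late visits, where b is largest, may be sparse. The settings at 24 and 36 months show the same pattern.
- The 3.1-point figure comes from mild-to-moderate patients, whereas TTP488-301 entry required MMSE 21 to 26.

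**Conclusion.** The concern holds. Under the baseline in SAP Section 5 and protocol 9.0, the between-arm ANCOVA conditions on a post-randomization score. In the main calculation only (1 − b) of a maintained benefit remains, at most 22% of it in the favourable direction (1 − 0.78), and the sign can reverse. Near zero is therefore a range, −0.9 to +0.5 points for the two Phase 2 differences, and exactly zero only at b = 1. Full catch-up appears as +2.4 to +4.5 against the azeliragon-first group.

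The identity in Step 1 needs no variance assumptions; the ranges rest on the assumed SDs and on no selection among enrolling completers. Confidence is high that the text is unreconciled and that the anchor has this effect. Because the analysis is descriptive and secondary, this is a point that should be fixed, not one that undermines the study's primary safety purpose.

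**What to change.** In SAP 5.1.1 and 5.1.2, name baseline (1) of Section 6.1, the last value before the first double-blind dose, as both reference and covariate for the ANCOVA between TTP488-301 arms, wherever it was collected. Confirm availability measure by measure; the documents do not show such a value for DEMQOL-Proxy or Aβ. Where none exists, summarize by arm without claiming a between-arm effect.

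Keep change from the open-label baseline as a within-group description. Report the LS-mean difference between arms with its 95% CI. State that it covers only TTP488-301 completers who enrolled, so randomization is not fully preserved; changing the anchor does not cure that selection.

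Reconcile Sections 5 and 6.1, and record the choice in SAP 1.9 as a change from protocol 9.0.

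The cost is a few sentences, one changed baseline variable in the program and the availability check. Section 5.1.1 already brings in the TTP488-301 data.

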9.1 POPULATIONS OF ANALYSIS

Populations of analysis are defined as follows:

- The full analysis set (FAS) includes all enrolled patients with on-treatment data. The FAS is used for all efficacy analyses.
- The per-protocol set (PPS) includes all FAS patients who are not excluded due to a significant protocol violation, where a significant protocol violation is one that has the potential to affect analysis conclusions. Final determinations of significant protocol violations will be made at the final blind data review meeting in accordance with guidance from ICH E9 (Statistical Principles).
- The safety set (SAF) includes all patients who received at least one dose of study medication. The SAF is used for all safety analyses.

To understand the impact of subjects who withdraw from the study prior to completion, the FAS will be partitioned into groups of subjects who complete the study (completers) and subjects who do not complete the study (dropouts).

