9.5 HANDLING MISSING DATA

In general, no imputation of values for missing data will be performed, except as otherwise described for efficacy evaluation. Standard clinical monitoring and data management practices will be used to ensure the integrity of data.

Sensitivity analyses will be done to assess the impact of missing data or spurious data on study conclusions. Sensitivity analyses will include methods of imputation, which will be defined in the SAP. Methods of imputation may include favorable imputation (regardless of treatment), unfavorable imputation (regardless of treatment), last-observation-carried-forward, and worse-observation-carried-forward; baseline values will not be carried forward.

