1.5 Study Design

This is an open-label extension study in patients with mild Alzheimer's disease who have successfully completed participation in the azeliragon Phase 3 TTP488-301 (STEADFAST) trial. Patients may receive azeliragon 5 mg/day for up to 2 years.

Participants were required to continue to be on SoC of a stable background acetylcholinesterase inhibitor therapy and / or memantine and continue the therapy for the duration of the trial, unless the investigator judges that the dose needs to be reduced or stopped due to a safety and/or tolerability reason.

Subjects were expected to participate in approximately 9 outpatient visits including baseline which is the same visit at the Month 18 visit in the TTP488-301 study.

Protocol TTP488-301 included two studies with a common infrastructure (A-study and B-study). Participants from either study are allowed to roll over into this open-label extension study.

A-study is conducted at multiple sites in the US and Canada. B-study is conducted at multiple sites in the US, Canada, Ireland, UK, South Africa, New Zealand, and Australia.

This study was terminated prematurely before participation outside of the US and Canada began; therefore, this study is conducted at multiple sites in the US and Canada.

The overall structure of the study includes the following periods:

Baseline Study Period: (Month 18 visit of TTP488-301): At the Month 18 visit of TTP488-301, subjects who met eligibility requirements were offered enrollment into this open-label extension study. Subjects had baseline assessments for efficacy and safety measures, including PK assessments.

Treatment Period: (Day 1 (Month 18 visit of TTP488-301) — Month 24): Subjects were treated with open-label azeliragon 5 mg QD. Efficacy and safety measures were taken. Blood samples were taken and subjects have assessments for safety and PK.

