6.2 Missing Data

In general, missing clinical data will not be imputed, except where explicitly defined. In the event of study withdrawal, a subject's final assessment will be used as the endpoint value, if applicable. For Trail Making Test A & B, if the assessment was not done due to cognitive reasons, the max score would be imputed. Note that the reason for "not-done" assessment is captured in the eCRF, and the specify field provides reason why. If the reason relates to cognitive reasons, the maximum time for Trails A (150 seconds) or for Trails B (300 seconds) is used.

Data are considered to be "on-treatment" if the assessment or collection follows the first administration of study medication and if the assessment occurs within 45 days following the final administration of study medication, justified based on the long half-life of this drug.

Dates with missing fields will not have days imputed.

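### The planned efficacy ANCOVA names no visit and has no repeated-measures structure, so its late-visit or endpoint means can understate decline or lose precision

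*SAP*

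**What the plan says.** **Model.** SAP 5.1.1 analyses change from baseline in ADAS-cog and CDR-sb by parent-study arm: "The ANCOVA will include baseline measure as a covariate and treatment arm from TTP488-301; a main-effects model will be used". There is no visit term, no within-subject covariance and no named analysis visit. Observed values and changes are to be summarised by group "at each individual time point and at endpoint (final on-treatment assessment for each subject", and least-squares means (LSMs) get 95% confidence intervals. SAP 5.1.2 carries similar methods to the other scales.

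**Missing data.** SAP 6.2 states: "In general, missing clinical data will not be imputed, except where explicitly defined". The one explicit substitution is the maximum time for Trail Making Tests not done for cognitive reasons. When a subject withdraws, the "final assessment will be used as the endpoint value, if applicable".

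**Early closure.** SAP 1.5 records: "This study was terminated prematurely before participation outside of the US and Canada began".

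**What the protocol promised.** Protocol 9.5 says: "Sensitivity analyses will include methods of imputation, which will be defined in the SAP". Protocol 9.1 adds: "To understand the impact of subjects who withdraw from the study prior to completion, the FAS will be partitioned into groups", namely completers and dropouts. The SAP defines no imputation sensitivity analysis and does not carry the split forward. SAP 1.9 nevertheless declares: "There are no modifications from the Statistical Section of the Protocol".

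**The concern.** An ANCOVA without a visit structure has to be run on one score per subject. The SAP leaves two candidates, and each has a weakness.

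- **By visit.** Each LSM uses only subjects tested at that visit. The scores of subjects who stopped earlier do not inform it, although in a progressive disease they predict where those subjects were heading.
- **At endpoint.** Every subject contributes a last on-treatment score, but after different lengths of follow-up. The mean then belongs to no particular month.

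The secondary objective is the time course on ADAS-cog and CDR-sb (SAP 1.1), and everyone receives azeliragon, so within-arm profiles are a main product. SAP 5.1.1 also compares former placebo subjects' profile in TTP488-301 with their profile in TTP488-303. Entry required completion of TTP488-301 through Month 18 (Protocol 4.1). If that comparison is made in enrollees, the first segment has no dropout and the second does, so selective loss would flatten only the second.

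For the Phase 2 study, Protocol 1.1.3 reports ANCOVA with multiple imputation, then LOCF and GEE analyses to show robustness. The SAP has no counterpart here.

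**Working it through.** The documents give no sample size, standard deviation, decline rate or dropout rate for TTP488-303, so there is no planned figure to reproduce. All inputs below are assumptions except the ADAS-cog visits (Months 3, 6, 9, 12, 18, 24), which follow the Schedule of Activities.

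**1. Three estimators of the Month 24 mean**

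Assumed: 300 subjects in two equal arms, true mean change 8 points, SD of subject slopes 7 points per 24 months, residual SD 3.5, 150 replicates, no early closure. Dropout after a visit is either unrelated to decline, or has log-odds rising by 0.5 (moderate) or 1.0 (strong) per 5 points of excess decline at the previous visit.

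- Observed-case: regress Month 24 change on baseline and arm among subjects seen at Month 24.
- Endpoint: mean of each subject's last score.
- Likelihood: multivariate normal over all six visits, unstructured covariance, baseline and arm effects at each visit.

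| Dropout achieved | Link to decline | True | Observed-case | Endpoint | Likelihood |
|---|---|---|---|---|---|
| 20% | none | 8.00 | 8.00 | 7.00 | 7.99 |
| 40% | none | 8.02 | 8.02 | 6.02 | 8.02 |
| 60% | none | 8.01 | 8.02 | 4.86 | 8.00 |
| 21% | moderate | 8.00 | 7.55 | 7.03 | 8.01 |
| 42% | moderate | 7.98 | 7.03 | 6.01 | 7.97 |
| 62% | moderate | 8.02 | 6.39 | 5.03 | 8.03 |
| 27% | strong | 8.01 | 6.89 | 6.88 | 8.00 |
| 47% | strong | 7.99 | 5.93 | 5.98 | 8.00 |
| 64% | strong | 8.00 | 4.97 | 5.07 | 7.94 |

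Subtracting from the true column, the observed-case shortfall is nil with no link, 0.45 to 1.63 with a moderate link and 1.12 to 3.03 with a strong one. The endpoint shortfall is about 1.0 to 3.2 in every row, including those where dropout is unrelated to decline.

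**2. Hand check of the endpoint result (40% dropout, no link)**

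Dropout per interval is h = 1 − 0.6^(1/5) = 0.097, and q = 1 − h = 0.903. A last score at Month 3, 6, 9, 12 or 18 loses 21, 18, 15, 12 or 6 months.

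Mean months lost = h(21 + 18q + 15q² + 12q³ + 6q⁴) = 6.05.

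Shortfall = (8/24) × 6.05 = 2.0 points, as in the table.

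**3. Month 18 with staggered closure**

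Assumed: 400 subjects, decline 6 points per year (true Month 18 change 6 × 1.5 = 9.0), SD of slopes 5, residual SD 3, dropout 1% or 2% per month multiplied by exp(0.5 × excess change/5), closure uniform over Months 3 to 24. Closure alone leaves (24 − 18)/(24 − 3) = 29% of subjects able to reach Month 18, about 114 of 400.

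| Dropout per month | Observed-case bias | Likelihood bias | SD observed-case | SD likelihood |
|---|---|---|---|---|
| 1% | −0.44 | +0.05 | 0.83 | 0.72 |
| 2% | −0.90 | −0.02 | 0.87 | 0.74 |

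These come from 60 replicates, so the Monte Carlo error of each mean is about 0.83/√60 = 0.11. Repeat runs gave observed-case biases of −0.5 to −0.6 and −1.0, with likelihood biases of 0.05 or less. The fair summary is 0.4 to 1.0 points, or 0.4/9.0 = 4% to 1.0/9.0 = 11% of the true change.

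Precision: 1 − 0.72/0.83 = 13% and 1 − 0.74/0.87 = 15% smaller standard error for likelihood. Repeat runs under staggered closure ranged from 12% to 40%. The gain persisted when dropout was unrelated to decline, where observed-case bias was negligible.

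**The case against.** The strongest reply is that this analysis carries little weight. The primary objective is safety, SAP 5.1 calls the efficacy analysis descriptive and allocates no alpha, and Protocol 9.0 places the key analysis in an integrated plan with TTP488-301. That plan is not among these documents and may contain a longitudinal model. This lowers the stakes and means no error rate is affected. It does not remove bias or imprecision from the LSMs and intervals this SAP itself will report.

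Some stronger readings are tempting and should be resisted.

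- **The arm comparison is biased.** A reader might infer this because the ANCOVA is the arm comparison. It does not follow: if dropout and its link to decline are alike in both arms, the two means shift together and the difference is not biased.
- **Early closure biases the means.** Closure on a calendar date is not obviously related to decline. Unless it is, it costs precision only.
- **The bias would pass for stabilisation.** Under the staggered-closure assumptions a 9.0-point decline would read as 8.0 to 8.6, which is still plain decline.
- **Subjects who stopped are thrown away.** Their scores stay in the summaries of the visits they attended and in the endpoint summary. What is lost is their contribution to late-visit estimates.

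The likelihood model's good showing is also partly built in, because the dropout in step 1 depends only on observed scores. If it depends on unobserved decline, that model is biased too.

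**Conclusion.** The point holds in a conditional form. The SAP leaves the analysis visit open, and both available readings are inferior to a model using all visits. By-visit LSMs understate mean decline if faster decliners leave, and are less precise than they need be in any case. Endpoint LSMs understate decline at a fixed time whenever subjects stop early.

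The affected outputs are the within-arm time courses and the former-placebo profile comparison. Bias in the arm difference would need differential dropout, for which the documents give no evidence.

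The sizes depend wholly on assumed inputs. The Month 24 table assumes no early closure, so it ranks the estimators and does not forecast the study.

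The gap between the documents needs no assumptions: the protocol assigns the imputation sensitivity methods to the SAP and plans the completer/dropout split, and the SAP supplies neither while declaring no modifications. The change is worth making, but the safety objective does not depend on it.

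**What to change.** For ADAS-cog, CDR-sb and the scales in SAP 5.1.2, make the main model a likelihood-based repeated-measures model of change from baseline at all scheduled post-baseline visits:

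- Terms: arm, visit, arm-by-visit, baseline, baseline-by-visit.
- Covariance: unstructured, with a named simpler structure if it fails to converge.
- Visits: only those with enough subjects, by a stated minimum. For ADAS-cog, first reconcile SAP 4.1.3.1, which adds Months 15 and 21, with the schedule in SAP 12, which does not.
- Output: visit LSMs and arm differences with 95% confidence intervals, and numbers observed by visit and arm.
- State how the rank alternative in SAP 5.1.2 would apply alongside this model.

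Keep the observed-case ANCOVA (visits named) and the endpoint ANCOVA as sensitivity analyses. Define the imputation analyses promised in Protocol 9.5 and restore the completer/dropout split of Protocol 9.1. In both, separate subjects cut off by study closure from those who withdrew. Correct SAP 1.9 accordingly.

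The cost is SAP text and some standard programming; no new data are needed, and the main model is compatible with the no-imputation rule. The drawback is reliance on missing-at-random, which is still a weaker assumption than taking the subjects who remain to represent everyone.
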